- Baseline: During the baseline phase cognitive function, cerebrovascular hemodynamics, grip strength test, pegboard dexterity test, 30 second chair sit stand test, 4 meter walk test, physical functioning scale of the Short Form 36 (SF-36) serum basic chemistry panel, plasma oxidized LDL, total antioxidant status, IL1-β, IL-6, Creactive protein and TNF-α and venous blood gas will be performed and the GI symptom questionnaire will be assessed. Spot urine will be collected for albumin to creatinine ratio. Demographics, medical history and physical will be performed.
- Randomization: Participants will be randomized with a 1:1 allocation ratio to treatment and placebo group using block randomization. Block randomization will be based on sex, age (within 5 years) and CKD stage (3b or 4). List of randomization will be generated by the study statistician and sent to the study pharmacist (A) Green Mountain Pharmaceutical, Denver, CO, and/or B) University of Colorado Research Pharmacy) blinded to the PI. Study investigators, healthcare providers, participants, data collectors, outcome adjudicators and data analysts will be blinded to treatment assignment.

- Follow-up: The follow-up schedule includes:
 - 1, 2, 4, 5, 7, 8, 10, and 11 months: safety check-in call via phone to complete adverse event assessment and GI symptom questionnaire
 - 3 and 9 months: safety visit (basic chemistry panel, adverse event assessment, GI symptoms questionnaire, BP, pill compliance).
 - 6 months: 1) Adverse event assessment, GI symptoms questionnaire, BP, pill compliance; 2) outcome measures: cognitive function, grip strength test, pegboard dexterity test, 30 second chair sit stand test, 4 meter walk test, physical functioning scale of the SF-36, serum basic chemistry panel, plasma oxidized LDL, total antioxidant status, IL1-β, IL-6, C-reactive protein and TNF-α; 3) spot urine for albumin to creatinine ratio.
 - 12 months: 1) Adverse event assessment, GI symptoms questionnaire, BP, pill compliance; 2) outcome measures: cognitive function, cerebrovascular hemodynamics, grip strength test, pegboard dexterity test, 30 second chair sit stand test, 4 meter walk test, physical functioning scale of the SF-36serum basic chemistry panel, plasma oxidized LDL, total antioxidant status, IL1-β, IL-6, C-reactive protein and TNF-α and venous blood gas; 3) spot urine for albumin to creatinine ratio.

Table 1		
Inclusion Criteria	Exclusion Criteria	

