Rationale for sodium bicarbonate dose: A dose of 0.5 mEq/kg-LBW/day has been shown to be safe and effective for treatment of metabolic acidosis in patients with CKD.^{49,53-54} Previous studies using this dose of sodium bicarbonate have not reported significant changes in edema, body weight or BP.^{49,53-55} In our **preliminary data**, sodium bicarbonate administration was not associated with an increase in BP or fluid gain in patients with CKD stage 3b-4.⁴⁹ Additionally, we will dose sodium bicarbonate based on LBW, not actual body weight. The volume of distribution of bicarbonate is approximately that of total body water. Total body water is dependent on lean body mass. Standard equations will be used to determine LBW.⁵⁶

b) Placebo: Subjects randomly assigned to placebo will take the same number of capsules as if they were assigned to receive 0.5 mEq/kg-LBW/day of sodium bicarbonate. Participants will take ½ the daily dose in the morning and the other ½ in the evening. The number of capsules will be rounded to the nearest whole capsule. To reduce pill burden and increase compliance the maximum number of pills per day will be six.

Rationale for placebo: A placebo group is necessary to successfully complete our aims. If a placebo group were not included both the investigators and participants would know that they are receiving sodium bicarbonate, which could influence medical management and perception of side effects in the study.

Dose Titration of Study Drug: If at month 3 the serum bicarbonate level not $\ge 23 \text{ mEq/L}$, we will increase the dose of sodium bicarbonate to 0.8 mEq/kg/LBW. This dose was recently used in a randomized trial comparing the safety and efficacy of doses of sodium bicarbonate therapy and was found to be well tolerated without any significant differences in adverse events or hospitalization compared with placebo.⁵⁷

5. Rationale for study duration. Changes in cognitive function, cerebrovascular reactivity and pulsatility can be seen within 4-6 weeks in adults 50 years and older but may require longer periods of time and published data use a period of 3 months to 1 year.⁵⁷⁻⁶¹ Hence, we are proposing a 12-month intervention.

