- Cognitive Function: Cognitive function will be assessed using the NIH Toolbox-Cognition Battery computerized tests⁶² at baseline, 6 months, and 12 months. The NIH Toolbox-Cognition Battery entails seven computerized tests that assess five major cognitive subdomains including: 1) attention, 2) episodic memory, 3) working memory, 4) language, 5) executive function, and 6) processing speed. Administering the NIH Toolbox cognitive battery will yield the following summary scores, in addition to individual measure scores: Cognitive Function Composite Score ('g' factor, or general cognitive ability based on performance of each subdomain), Fluid Cognition Composite Score (includes tests of attention, executive function, working memory, and processing speed) and Crystallized Cognition Composite Score (includes Picture Vocabulary and Reading Recognition measures). These instruments have been validated in 476 participants ranging in age from 3 to 85 years, with representation from both sexes, 3 racial/ethnic categories and 3 levels of education.⁶² In addition, the Trail Making Test (TMT) parts A and B will be administered to determine processing speed and executive function, respectively.⁶³ The investigative team has experience administering these assessments.⁶⁴
- Justification for primary outcome: Our preliminary data suggests that correction of acidosis may improve cerebrovascular function. The use of the NIH Toolbox and the TMT parts A and B allow for assessing cognitive function in approximately 30-45 minutes and has been validated in numerous patient populations. Our research group has experience with these cognitive function measurements.⁶⁴

b) Secondary Outcomes

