8. Power and Statistical Analysis: Briefly, in this pilot study a total of 50 patients will be enrolled and equally randomized to the two groups. The two-sample t-test is applicable to compare the change between the two groups for each cognitive function subdomain and is the basis for power analysis. This sample size was determined based on feasibility and availability, not a specified statistical power. With a two-sided type I error rate of 0.05, the study will have a power of 79% to detect an effect of 0.80 if 25 patients per group can be included in the final analysis. This power calculation applies to the secondary and other outcome variables. For Aim 1, we will assess the treatment effect on each of the six subdomains of cognitive function by a linear regression model with the measure at end of study regressed on treatment along with the baseline measure of the subdomain, sex, age, and baseline eGFR. Conclusion will be subdomain specific. For Aims 2 and 3, the linear regression model will be used to examine the treatment effect on the secondary and other outcomes. Particularly, the measure of an outcome variable at end of study will be regressed on intervention indicator and baseline measure of the outcome variable plus sex, age and baseline eGFR for adjustment purpose.

9. Potential Problems and Alternative Strategies

- Although subject recruitment and retention are always challenging, we should be able to complete the study in the proposed timeline given our groups excellent track record in recruiting participants in clinical trials.
- We should have few difficulties with the proposed experimental procedures and protocols as they are already established in the vascular laboratories at the KDRC by [name].
- We recognize that alternative approaches exist for examining the effects of alkali therapy on cognitive function in patients with CKD. For example, one alternative would be to undertake a larger study to examine structural changes with brain MRIs rather than the investigation proposed in the current application. However, our proposed study is the most cost-effective approach to obtain confirmation of the study hypotheses.

- We recognize that different dosages of sodium bicarbonate therapy can be used. However, the proposed dose in the current study has been shown to be safe and effective in treating metabolic acidosis in CKD 3-4.

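### The 6-month outcome assessments have no role in the stated analysis, so participants who leave after month 6 are lost to the 12-month comparison and no 6-month effect is planned

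*Combined protocol and SAP*

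**What the plan says.** In section IV (Research Methods), the 6-month entry of the follow-up schedule lists "outcome measures: cognitive function, grip strength test, pegboard dexterity test". It goes on to the chair-stand and walk tests, the SF-36 physical functioning scale, and the oxidative stress and inflammation markers. Section 7a repeats the timing for the primary outcome: cognition is assessed "at baseline, 6 months, and 12 months". Cerebrovascular measures are taken only at baseline and month 12.

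Section 8 (Power and Statistical Analysis) gives one model. For Aim 1 it is "a linear regression model with the measure at end of study regressed on treatment along with the baseline measure of the subdomain", plus sex, age and baseline eGFR. Aims 2 and 3 use the same form. The power statement rests on a two-sample t-test of one change per patient.

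The Specific Aims are all framed as a comparison of baseline with 12 months. No 6-month comparison, repeated-measures model, missing-data method or descriptive role for month 6 is stated. The nearest text is the food-frequency passage in the justification for secondary outcomes. It speaks loosely of associations with diet during the study and does not name month 6.

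**The concern.** Scheduled outcomes with no assigned use raise three issues.

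- **Missing data.** The Exit Criteria allow withdrawal at any time and exit for side effects or non-compliance. Under the stated regression, someone with baseline and 6-month scores but no 12-month score drops out of the analysis. The power statement holds "if 25 patients per group can be included in the final analysis", which is everyone enrolled, so no loss is allowed for.
- **Timing.** The pilot is meant to inform a larger trial. The rationale for study duration leaves the onset of effect open: it says that "Changes in cognitive function, cerebrovascular reactivity and pulsatility can be seen within 4-6 weeks in adults 50 years and older", and the same sentence then allows that more time may be needed. The 6-month contrast is the only cognitive evidence on timing that this trial will hold before month 12, and the plan does not estimate it.
- **Selective reporting.** With conclusions drawn separately for six cognitive subdomains, an unassigned second time point leaves open which 6-month results are shown once the data are known.

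**Working it through.** **Inputs from section 8.** "a total of 50 patients will be enrolled and equally randomized to the two groups"; "With a two-sided type I error rate of 0.05"; "the study will have a power of 79% to detect an effect of 0.80"; 25 analysed per group. The units of the 0.80 are not given and are read as standard deviations (SD).

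**Assumed, because the documents do not give it.** An equal correlation r between any two visits, from 0.5 to 0.8; loss of 10% or 20% of participants after month 6, equal in the two arms.

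**1. The plan's own figure.** Noncentral t, 25 per group, effect 0.80, 48 degrees of freedom: power 79.1%, against the stated 79%. The normal approximation gives 80.7%. The figure reproduces.

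**2. What the model uses.** Complete follow-up yields 50 × 2 = 100 post-baseline cognitive assessments. The end-of-study regression uses 50, and the 50 from month 6 enter no stated estimate. The same count applies to the physical tests and the Aim 3 markers.

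**3. Complete data, 12-month target.** A two-visit model with visit-specific treatment and baseline effects and unstructured covariance was compared with the 12-month regression in 200 simulated data sets. The largest difference in the 12-month effect was 3e-15, so the two are the same estimate. If some covariate slopes are shared across visits, the results are close but not identical.

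**4. 12-month target with loss after month 6.** The partial correlation of months 6 and 12 given baseline is p = (r − r²)/(1 − r²). With a share m missing at month 12, the variance relative to the complete-case regression is 1 − m·p².

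| r | p | p² | ratio, m = 10% | ratio, m = 20% |
|---|---|---|---|---|
| 0.5 | 0.333 | 0.111 | 0.989 | 0.978 |
| 0.7 | 0.412 | 0.170 | 0.983 | 0.966 |
| 0.8 | 0.444 | 0.198 | 0.980 | 0.960 |

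For power (normal approximation, effect 0.80), the complete-case size per arm is 25(1 − m), and the repeated-measures equivalent is that number divided by the ratio.

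- m = 10%: 22.5 per arm gives 76.5%. The equivalent 22.8 to 23.0 gives 77.0% to 77.3%.
- m = 20%: 20 per arm gives 71.6%. The equivalent 20.5 to 20.8 gives 72.5% to 73.3%.

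**5. A different target: the average of months 6 and 12.** The residual variance is 1 − r² for month 12 alone and (1 + r)/2 − r² for the average. The ratios are 0.50/0.75 = 0.67 at r = 0.5, 0.36/0.51 = 0.71 at r = 0.7, and 0.26/0.36 = 0.72 at r = 0.8.

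The average has more power only if the 6-month effect exceeds a fraction 2√ratio − 1 of the 12-month effect, which is 0.63 to 0.70. At r = 0.7, read 0.80 as SDs of change, so the raw effect is 0.80 × √(2 × 0.3) = 0.62 SD. Power is then 85% for month 12 alone. For the average it is 95% if the two effects are equal, 77% if the 6-month effect is half, and 43% if it is nil.

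**The case against.** The strongest reply is that the planned regression already answers the stated question. All three aims concern 12 months, and step 3 shows that with everyone followed the 12-month estimate does not improve. That stands, and it rules out two stronger readings.

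- **That the trial throws away half of its information.** Half is a count of assessments. It is not half the information on the 12-month effect, and the stated power is not wrong.
- **That an effect ought to be visible at month 6, so averaging the visits would buy substantial power.** The duration rationale also says that longer may be needed, and gives this as the reason for 12 months. The documents offer no evidence that the 6-month effect reaches 63–70% of the 12-month effect. They also give no correlations. If months 6 and 12 correlate at 0.85 and each correlates with baseline at 0.7, the variance ratio for the average is about 0.85, not 0.71.

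It can also be said that section 8 is expressly brief, that month 6 could still be reported descriptively, and that further contrasts across six subdomains add multiplicity. The last point is fair and is met by labelling. The first two do not supply the missing statement of what month 6 is for, or keep early leavers in the 12-month analysis.

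**Conclusion.** The point holds as a modest improvement worth making. Outcomes measured at 6 months have no stated use, and a participant seen at month 6 but not at month 12 is lost to the treatment comparison. This reads end of study as month 12; section 8 does not define the term, but the aims support that reading.

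For the 12-month contrast, the gain exists only when month-12 values are missing. It is 1–2% less variance at 10% loss and 2–4% at 20% loss, or roughly 0.5 to 2 power points, for r between 0.5 and 0.8. There is also less bias if dropout depends on the 6-month score, under a missing-at-random assumption. That benefit cannot be sized from the documents.

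The other benefit is a pre-specified 6-month estimate for planning the larger trial. The precision of a 6/12-month average is not a reason for the change, because it belongs to a different question and turns into a loss if benefit comes late.

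**What to change.** In section 8, for outcomes measured at both 6 and 12 months (cognition, physical function, Aim 3 markers):

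- Fit one repeated-measures model with treatment, visit, treatment-by-visit, baseline score, baseline-by-visit, sex, age and baseline eGFR, and an unstructured within-person covariance.
- Keep the 12-month treatment contrast as the primary estimate. State that participants with a 6-month but no 12-month value contribute under a missing-at-random assumption.
- Report the 6-month contrast with a confidence interval as supportive, to inform the timing and duration of the larger trial.
- If a 6/12-month average is reported at all, describe it as optional and as answering a different question.
- Keep the single-time regression for the transcranial Doppler outcomes, which have no 6-month measure.
- Define end of study as month 12, if that is what is meant.

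The cost is a few sentences and a slightly longer model. No visits, tests or patients are added. The price is more contrasts per outcome, which must be labelled as not confirmatory.

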 Age 50-80 years old Serum bicarbonate 16-22 mEq/L on 2 separate measurements (at least 1 day apart) CKD stage 3b or 4 at time of screening (eGFR 15-44 ml/min/1.73m²) Blood pressure <140/90 mm Hg prior to randomization Stable anti-hypertensive regimen for at least one month prior to randomization Montreal Cognitive Assessment Score > or = 24 No history of stroke No history of neurologic disease Able to provide consent 	 Significant comorbid conditions that lead the investigator to conclude that life expectancy is less than 1 year Use of chronic daily oral alkali within the last 3 months (including sodium bicarbonate, calcium carbonate or baking soda) Uncontrolled hypertension Serum potassium < 3.3 or ≥ 5.5 mEq/L at screening New York Heart Association Class 3 or 4 heart failure symptoms, known EF ≤30%, or hospital admission for heart failure within the past 3 months Factors judged to limit adherence to interventions Anticipated initiation of dialysis or kidney transplantation within 12 months Current participation in another research study Pregnancy or planning to become pregnant or currently breastfeeding Chronic use of supplemental oxygen 	
4 Study Drug Dosing The study drugs (bicarbonate and the matched placebo) will be		

4. Study Drug Dosing. The study drugs (bicarbonate and the matched placebo) will be prepared by A) Green Mountain Pharmaceutical and B) University of Colorado Research Pharmacy and will be identical in size, color, shape and taste. Each sodium bicarbonate capsule contains 7.7 mEq of bicarbonate and 178 mg of sodium. The matching placebo capsule will contain cornstarch. Green Mountain Pharmaceutical and/or University of Colorado Research Pharmacy will bottle the capsules and label the bottles with code numbers to maintain the study's double blind and Green Mountain Pharmaceutical will ship the bottles directly to the investigative site. Study drug supplied by the on-campus pharmacy will be managed and picked up directly from University of Colorado Research Pharmacy for each study participant.

. . .

a) Sodium bicarbonate: Subjects randomly assigned to sodium bicarbonate therapy will receive 0.5 mEq/kg-lean body weight (LBW)/day for the entire 12 months. Participants will take ½ the daily dose in the morning and the other ½ in the evening. The number of capsules will be rounded to the nearest whole capsule. To reduce pill burden and increase compliance the maximum number of pills per day will be six.

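### The month-3 titration raises only the sodium bicarbonate dose while placebo stays tied to the 0.5 mEq/kg capsule count; read literally, a capsule increase would reveal the arm

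*Combined protocol and SAP*

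**What the plan says.** All references are to the combined protocol and SAP, section IV unless stated.

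- **Study Drug Dosing, (a) Sodium bicarbonate:** the active arm "will receive 0.5 mEq/kg-lean body weight (LBW)/day for the entire 12 months".
- **Study Drug Dosing, (b) Placebo:** placebo participants "will take the same number of capsules as if they were assigned to receive 0.5 mEq/kg-LBW/day of sodium bicarbonate".
- **Dose Titration of Study Drug:** if the month-3 serum bicarbonate is not at least 23 mEq/L, "we will increase the dose of sodium bicarbonate to 0.8 mEq/kg/LBW".
- **Both arm paragraphs:** "Participants will take ½ the daily dose in the morning and the other ½ in the evening", with rounding to whole capsules, and "the maximum number of pills per day will be six". Each active capsule holds 7.7 mEq.
- **Randomization:** "Study investigators, healthcare providers, participants, data collectors, outcome adjudicators and data analysts will be blinded to treatment assignment". On allocation: "List of randomization will be generated by the study statistician and sent to the study pharmacist".
- **Study Drug Dosing, opening paragraph:** the pharmacies will bottle the capsules and "label the bottles with code numbers to maintain the study's double blind". Study drugs are defined there as bicarbonate and its matched placebo.

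The titration paragraph mentions neither placebo capsules, nor the six-capsule maximum, nor who carries out the change.

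**The concern.** The placebo rule and the titration rule cannot both be followed without separating the arms. If placebo capsules stay at the 0.5 count and only sodium bicarbonate is raised, a rise in capsule count after month 3 can happen in one arm only. Anyone who knows the rule and sees the rise knows the allocation. Someone who sees a month-3 value below 23 and no rise could infer placebo, at body weights where a rise would be expected.

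That second inference matters because everyone enters at 16-22 mEq/L (Table 1), below the trigger. The safety monitoring section also expects values to fall particularly on placebo. Many placebo participants would therefore probably meet the trigger and, on the literal text, receive no change.

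At stake is the blind ahead of the 12-month cognitive assessment. Section 8 (Power and Statistical Analysis) regresses the end-of-study measure on treatment, its baseline and covariates. The protocol's own reason for using a placebo is that knowing the treatment could affect management and the perception of side effects.

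A secondary issue is the delivered dose. The capsule maximum is stated only alongside the 0.5 mEq/kg dose, so a reader cannot tell whether it limits the titrated dose.

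**Working it through.** The plan gives no figure of its own on this point. Its one sample-size figure, 79% power, reproduces (79.1% by the noncentral t with 25 per group and effect 0.80) and plays no part here.

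**1. The passages side by side.**

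| Reading of the titration rule | Placebo sentence (0.5 count) | Active sentence (0.5 for 12 months) | Blinding statement |
|---|---|---|---|
| Bicarbonate arm only (literal) | Consistent | Not reconciled | In conflict: a rise occurs in one arm only |
| Matched change in both arms | Contradicted | Not reconciled | Consistent in principle |

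Neither reading satisfies every sentence.

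**2. How often the step would arise in the bicarbonate arm.** Input: the pilot crossover study in section III(b), 20 patients, 6 weeks at 0.5 mEq/kg-LBW/day, on-treatment mean 22.4 (SD 3.0) mEq/L. Assumptions: normal distribution, and the pilot carries over to month 3.

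- P(value < 23) = Φ((23 − 22.4)/3.0) = Φ(0.20) = 0.579; × 25 = 14.5 participants.
- Sampling error of the mean: 22.4 ± 1.96 × 3.0/√20 = 21.09 to 23.71. This gives 0.738 down to 0.406, or about 18 down to 10 of 25.
- If results are reported as whole numbers (assumption), the effective cut is 22.5: Φ(0.1/3.0) = 0.513, range 0.343 to 0.681.

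These ranges leave out uncertainty in the SD and chance variation among 25 patients, so they are too narrow.

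**3. Whether the capsule count would change.** Daily capsules = dose × LBW / 7.7, at most six, halves rounded up. The documents give no LBW distribution, so a range is shown. The text allows rounding of the daily total or of each half-dose.

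| LBW (kg) | Daily total rounded: 0.5 → 0.8 | Each half-dose rounded: 0.5 → 0.8 |
|---|---|---|
| 40 | 3 → 4 | 2 → 4 |
| 47 | 3 → 5 | 4 → 4 |
| 50 | 3 → 5 | 4 → 6 |
| 60 | 4 → 6 | 4 → 6 |
| 70 | 5 → 6 | 4 → 6 |
| 77 | 5 → 6 | 6 → 6 |
| 84.7 | 6 → 6 | 6 → 6 |

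- Daily total rounded: a rise of 1 to 3 capsules at every LBW from 30 kg to just under 84.7 kg, then none.
- Each half-dose rounded: a rise of 2 from 30 kg to just under 77 kg, except none at about 46.2-48.1 kg, then none.
- If the maximum does not apply after titration, the rise continues at higher weights. At 84.7 kg, 0.8 × 84.7/7.7 = 8.8, so nine capsules by daily total against six.

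**4. What the maximum would do to the titrated dose.** Six capsules supply 6 × 7.7 = 46.2 mEq/day. Before rounding, a full 0.8 mEq/kg is reachable only up to 46.2/0.8 = 57.75 kg LBW. Above that, six capsules supply 46.2/60 = 0.77, 46.2/70 = 0.66 and 46.2/80 = 0.58 mEq/kg.

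**The case against.** **A matched change was intended.** The titration heading refers to study drug, which the protocol defines as both products. The trigger names no arm, and the dose-reduction rules also act on study drug without naming an arm. This reading is plausible. It does not resolve the point, because the placebo sentence still holds placebo to the 0.5 count and no sentence provides a matching rise.

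**Nobody blinded needs to know the arm.** This stands. The pharmacist holds the list and the supply is coded, so blinded staff could forward every low value. A reader might infer that applying the rule forces an investigator to learn the allocation; the documents do not support that. However, nothing in the available text gives the step to the pharmacy, and on the literal rule the capsule count would still show the arm. The protocol refers to a human-subjects section that is not in the available text, so this absence is qualified.

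**The 12-month phrase is only a starting dose and a duration.** This largely stands. Other rules also halve or stop the drug, so the phrase cannot be absolute. It is the weaker part of the mismatch. The placebo sentence is the main part and changes no bicarbonate exposure, so a reader should not conclude that the active dose is inconsistent on every reading. Only the unclear reach of the capsule maximum affects the delivered dose, and as an unqualified statement it may well apply throughout.

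**The blind is already exposed, and the route to the scores is thin.** This partly stands. Whoever manages safety sees serum bicarbonate, which treatment moves, and what titration adds has not been isolated. Whether participants would know the rule is unknown. The coordinator who gives the cognitive tests also collects adverse events, but no passage has that person handling capsules, seeing chemistry results or applying the titration. The NIH Toolbox is computerised. The month-6 scores do not enter the stated model.

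**Conclusion.** The contradiction is in the text and needs no modelling. The placebo capsule rule and a titration sentence that names only sodium bicarbonate cannot both be followed without capsule increases being confined to one arm, and the 12-month dose statement is left unreconciled. On the literal reading, allocation could be revealed before the 12-month assessment.

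The step would not be rare: about 58% of the bicarbonate arm (41-74%) on the pilot figures, assuming normality and transfer to month 3. With the maximum of six, the count would change at most LBWs below 77 kg (half-dose rounding) or 84.7 kg (daily-total rounding).

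The capsule maximum is a secondary inconsistency. If it covers the titrated dose, 0.8 mEq/kg cannot be fully supplied above 57.75 kg LBW.

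A reader might go further and infer that the trial will be unblinded or that its false-positive rate is inflated. The documents support neither: a matched change may be what is done, a pharmacy channel exists, and no path to biased scores is demonstrated. The protocol also describes the study as not firmly confirmatory. The point is a contradiction that should be fixed, and the fix is cheap.

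**What to change.** The sponsor should reconcile the placebo capsule, titration, 12-month-dose and capsule-maximum passages with the blinding statement. The revised text should have any month-3 capsule change carried out through the coded pharmacy supply, so that neither a change nor its absence identifies the arm by rule. It should also say whether rounding applies to the daily total or to each half-dose, and whether the capsule maximum covers the titrated dose, so that the deliverable exposure is clear. No dose, trigger or titration rule is proposed here; those are for the sponsor.

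The cost is protocol wording, a pharmacy instruction, and possibly extra placebo capsules and pill burden. The change lowers the risk to the blind but does not remove it: if the arms meet the trigger at different rates, a capsule change will still carry some information about allocation.
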